### 3.3.2 Exclusion Criteria

Potential subjects meeting any of the following criteria will be excluded from enrollment:

[figure not shown]
1. CXCR4-tropic virus or Dual/Mixed tropic (R5X4) virus as determined by Trofile® DNA Assay at Screening Visit
2. Hepatitis B infection as manifested by the presence of Hepatitis B surface antigen (HBsAg)
3. Any active infection or malignancy requiring acute therapy (with the exception of local cutaneous Kaposi's sarcoma)
4. Laboratory test values of  $\geq$  grade 4 DAIDS laboratory abnormality
5. Females who are pregnant, lactating, or breastfeeding, or who plan to become pregnant during the study

6. Unexplained fever or clinically significant illness within 1 week prior to the first study dose
7. Any vaccination within 2 weeks prior to the first study dose.
8. Subjects who have failed on a maraviroc containing regimen.
9. Subjects weighing < 35kg
10. History of anaphylaxis to any oral or parenteral drugs
11. History of Bleeding Disorder or patients on anti-coagulant therapy (except aspirin)

**Note:** Subjects with well-controlled bleeding disorder while on stable anti-coagulant therapy dose with documented stable INRs can be enrolled as per discretion of the Investigator.

12. Participation in an experimental drug trial(s) within 30 days of the Screening Visit
13. Any known allergy or antibodies to the study drug or excipients
14. Treatment with any of the following:
  - a. Radiation or cytotoxic chemotherapy with 30 days prior to the screening visit
  - b. Immunosuppressants within 60 days prior to the screening visit
  - c. Immunomodulating agents (e.g., interleukins, interferons), hydroxyurea, or foscarnet within 60 days prior to the screening visit
  - d. Oral or parenteral corticosteroids within 30 days prior to the Screening Visit. Subjects on chronic steroid therapy > 5 mg/day will be excluded with the following exception:
    - o Subjects on inhaled, nasal, or topical steroids will not be excluded
15. Any other clinical condition that, in the Investigator's judgment, would potentially compromise study compliance or the ability to evaluate safety/efficacy

**Figure 3-1: Study Flow Diagram**

## 4 STUDY SCHEDULE

The study is divided into three phases: Screening, Treatment and Follow-up.

(1) **Screening Phase** (Screening to T1 Visit) begins with signing of Informed Consent and lasts up to 6 weeks. Subject will enter the Treatment Phase as soon as HIV-1 viral tropism results are available for review by Investigator.

**Treatment Phase** (T1 to T48 Visit) begins with Treatment Phase begins with an evaluation of results of laboratory samples collected at the Screening Visit. The first treatment (T1) visit will be administered within 42 days of the Screening Visit, with weekly visits ( $\pm 3$  days) thereafter. The first 300 eligible subjects were randomized 1:1 to receive either PRO 140 350mg weekly (Group A) or PRO 140 525mg weekly (Group B). Once the enrollment of 300 subjects was completed, additional subjects will be randomized 1:1 to PRO 140 525mg (Group B) or PRO 140 700mg (Group C).

All subjects will continue taking their existing ART during the Screening Phase and for first week of the Treatment Phase. After Week 1 of the Treatment Phase, subjects will stop their existing ART regimen and receive assigned dose of PRO 140 SC monotherapy.

Study participants will be regularly monitored for viral load following initiation of PRO 140, and will cease weekly study treatment injections should they experience virologic failure.

Subjects who experience virologic failure at any point during Part 1 of Treatment Phase will undergo the Virologic Failure (VF) Visit assessments and then exit the Treatment Phase to enter the Follow-up Phase of the study. unless subjects in Group A opt to enter Part 2 of Treatment Phase and receive PRO 140 525mg SC weekly injections or subjects in Group B opt to enter Part 2 of Treatment Phase and receive PRO 140 700mg SC weekly injections for remainder of 48-week Treatment Phase.

Subjects who do not experience virologic failure will enter the Follow-up Phase of the study at the end of 48-week Treatment Phase.

(2) **Follow-Up Phase:** The duration of follow-up depends on the status of viral load suppression.

- Subjects who experience virologic failure will be followed up every 4 weeks until viral suppression is achieved (i.e., plasma HIV-1 RNA levels to return to  $< 50$  copies/mL). Additionally, virologic failure subjects will return to clinic at 6 months and at one year from the time of the Virologic Failure (VF) Visit.
- Subjects who do not experience virologic failure at the end of 48-week Treatment Phase, will be followed up every 2 week for total of 4 weeks.

Procedures to be performed during each of these study phases are described below and provided as a Schedule of Assessments in [Table 4-1](#), [Table 4-2](#) and [Table 4-3](#).

**Table 4-1: Schedule of Assessments – Screening and Treatment Phase (T1 – T16)**

Procedure/Assessments	Visit	SV	Treatment Phase (T1 – T16)																In case of Treatment Failure VF
			T1		T2	T3	T4	T5	T6	T7	T8	T9	T10	T11	T12	T13	T14	T15	
Window Period			(Pre-Rx)	(Post-Rx)															
Informed Consent 	X																		
Eligibility Evaluation 	X																		
Pre-enrollment Eligibility		X																	
Subject Demographics	X																		
Medical History 	X	X																	
Physical Examination	X	X 		X 															
Neurological Assessment 		X																X	X
Vital Signs 	X	X	X	X	X	X	X	X	X	X	X	X	X	X	X	X	X	X	X
Body Weight & Height	X																		
ECG	X																		X
Complete Blood Count (CBC) 	X												X						X
Biochemistry 	X												X						X
Coagulation Indices	X												X						X
Serum Pregnancy Test 	X																		
Urinalysis 	X												X						X
Urine Pregnancy Test 		X																	
HBsAg	X																		
Plasma HIV-1 RNA level	X	X		X		X		X		X		X		X		X		X	X
TruCount T assay 	X	X		X		X		X		X		X		X		X		X	X
Trofile® DNA Assay	X											X							X 
Trofile® RNA Assay																			X 
HIV-1 Drug Resistance Assay 	X	X																	X
Serum concentration of ART drugs 						X				X				X					X
Randomization (via CTMS) 																			
PRO 140 Administration 																			
– Group A (350mg SC)		X		X	X	X	X	X	X	X	X	X	X	X	X	X	X	X	
– Group B (525mg SC)																			
– Group C (700mg SC)																			

Procedure/Assessments	Visit	SV	Treatment Phase (T1 – T16)																In case of Treatment Failure			
			T1 (Pre-Rx) (Post-Rx)		T2	T3	T4	T5	T6	T7	T8	T9	T10	T11	T12	T13	T14	T15	T16	VF		
Window Period			Within 6 weeks of SV			±3 days since last treatment																
Combination ART Regimen 	X		X																X			
Injection Site Reaction Assessment 				X	X	X	X	X	X	X	X	X	X	X	X	X	X	X				
Injection Site Pain Assessment (VAS) 					X	X	X	X	X	X	X	X	X	X	X	X	X	X				
PK sample for PRO 140 		X					X				X			X				X	X			
Anti-idiotypic antibodies to PRO 140 		X					X			X				X				X	X			
Measurement of treatment adherence 							X			X				X				X	X			
Adverse Events			X	X	X	X	X	X	X	X	X	X	X	X	X	X	X	X	X	X		
Concomitant Medications	X	X	X	X	X	X	X	X	X	X	X	X	X	X	X	X	X	X	X	X		
Potential Biomarkers																						
gp120 genotypes 		X																				
HIV-1 RNA Single Copy Assay 		X								X				X								
Immune Activation Markers 		X																	X			
PhenoSense® Entry Assay 		X										X							X			
CCR5 expression levels 		X																				
Quest Diagnostics Tropism Assay 	X	X 																	X			
CNS sub-study (n=20)																						
CSF sample collection 		X				X													X			
GU sub-study (n=20)																						
Genital Secretion sample collection 		X				X												X	X			
CCR5 Receptor Occupancy 		X		X		X		X		X		X		X		X		X	X			
CCR5 Genotyping 	X											X							X			

**Foot Notes:**

- [1] Informed consent must be obtained prior to patient participation in any protocol-related activities that are not part of routine care.
- [2] Initial evaluation of patient eligibility will be performed by Investigator.
- [3] Medical history, past surgeries, disease history, history of substance abuse, social history, blood transfusion history, and current therapies (medications and non-medications).
- [4] Symptom-directed physical examination at clinic visits.

- [5] The neurological assessment tool is based on the three question survey used by Simioni et al. (Simioni S, 2010). Additional neurological assessment modalities may be used as per Investigator's discretion.
- [6] Vital signs (blood pressure, heart rate, respiration rate, and temperature) will be measured at clinic visit. Note: Only post-treatment vitals will be measured beyond T2.
- [7] Hemoglobin, Hematocrit (HCT), Red Blood Cells (RBC), White Blood Cells (WBC) with total and differential count, Absolute Neutrophil Count (ANC) and platelets.
- [8] Serum Biochemistry  
Hepatic function indicators: total and direct bilirubin, alkaline phosphatase, aspartate aminotransferase (AST), alanine aminotransferase (ALT), total protein, Lactate dehydrogenase (LDH)  
Renal function indicators: BUN, creatinine  
Electrolytes: sodium, potassium, chloride, calcium and bicarbonate  
Other: glucose (random), cholesterol (total)
- [9] ONLY performed on women of childbearing potential.
- [10] Urine samples will be tested for color, appearance, specific gravity, pH, protein, glucose, occult blood, ketones, leukocyte esterase, nitrite, bilirubin, urobilinogen, and microscopic examination of urine sediment.
- [11] Includes: Absolute Lymphocytes, CD3 cell count, CD4 cell count, CD8 cell count, CD3%, CD4% and CD8% Monogram Biosciences GenoSure Archive Assay will be performed at Screening and prior to PRO 140 administration at T1 visit.
- [12] Monogram Biosciences GenoSure Archive Assay performed at SV and T1; PhenoSense® GT (and PhenoSense Integrase and GeneSeq Integrase testing, if applicable), will be performed at the time of virologic failure.
- [13] To assess subject compliance in abstaining from previous ART regimen after T2 visit
- [14] Study subjects will continue to take their existing antiretroviral regimen up to one week after receiving initial dosing of PRO 140. Subjects will re-initiate their previous antiretroviral regimen or an alternative regimen selected by their treating physician if virologic failure occurs or have met any other criteria for discontinuation of study treatment as specified in Section 5.2.1 of the protocol.
- [15] Injection Site Reaction Assessment as assessed by Investigator (or designee) at the clinic visits and by visiting nurse or qualified medical professional during home visits. Injection Site Reaction Assessment will not be applicable if PRO 140 is self-administered by subjects at home.
- [16] Subject-perceived injection site pain will be assessed using the Pain Visual Analog Scale (VAS) prior to study treatment administration which evaluates average pain since last treatment. Injection Site Pain Assessment will not be applicable if PRO 140 is self-administered by subjects at home.
- [17] Blood sample collected at T1 (prior to first dose of PRO 140), T4, T8, T12, T16 and VF visits
- [18] Treatment adherence self-reported by subject at T4, T8, T12, T16 and VF visits when subject comes to clinic.
- [19] Blood sample will be collected at T1 visit to assess the baseline gp120 genotypes from each enrolled subject to identify potential polymorphisms that may decrease PRO 140 susceptibility and may affect response to PRO 140
- [20] Blood sample collected at T1 (prior to first dose of PRO 140), T8 and T12 visits. Blood sample will be collected at T8 and T12 visit only if last known viral load result is "Target Not Detected" or < 40 copies/mL.
- [21] immune activation markers (CRP, IL-6, D-Dimer)
- [22] Monogram Biosciences HIV-1 PhenoSense® Entry assay with AMD3100 (X4 inhibitor drug), Maraviroc and PRO 140 (R5 inhibitor drugs). Sample collected for Trofile DNA/RNA at Screening will be used to test PhenoSense® Entry for eligible/enrolled subjects at Baseline.
- [23] Flow cytometry and the 2D7 MAb will be used to measure CCR5 expression levels on peripheral blood mononuclear cells (PBMCs)
- [24] Quest Diagnostics HIV-1 Coreceptor Tropism with Reflex to UltraDeep Sequencing or HIV-1 Proviral Tropism.
- [25] If assessment **not** performed at SV.
- [26] To evaluate PRO 140 concentration and HIV-1 RNA level in cerebrospinal fluid (CSF)
- [27] To evaluate PRO 140 concentration and HIV-1 RNA level in genital secretions

- 
- [28] Monogram Biosciences Trofile® DNA or RNA assay (or both) will be performed at the Virologic Failure Visit depending on the last known HIV-1 RNA levels.
  - [29] Randomization will occur via CTMS
  - [30] Should VF occur, Group A or Group B subjects may transition to high dose IP and continue in 48-week treatment phase.
  - [31] To assess the number CCR5 receptors on patients' CD4 cell surface, and number and percentage of CCR5 receptors that are covered by PRO 140. Sites should not collect samples on Fridays, since InCellDx lab cannot receive samples on Saturdays.
  - [32] No new sample collection needed. The residual whole blood sample collected for tropism assessment at Screening or at post-treatment visits will be used for testing of CCR5 genotyping (homozygous or heterozygous status).

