#### 7.10.12 HIV-1 Drug Resistance Assay

a. GenoSure Archive Assay

GenoSure Archive assay provides HIV-1 antiretroviral drug resistance data when standard resistance testing cannot be performed due to inadequate plasma viral load.

- Frequency of sample collection: At SV, T1, and T48. Additionally, at VF, VF-6mFU and VF12mFU Visits, if last known HIV-1 RNA level is <1000 copies/mL.

b. PhenoSense® GT

PhenoSense® GT is a combination resistance test for three classes of antiretroviral drugs (i.e., nucleoside/nucleotide, non-nucleoside, and protease inhibitors), that provides both phenotypic and genotypic results from the same blood sample (viral load  $\geq 500$  copies/mL).

- Frequency of sample collection: At VF, VF-6mFU and VF12mFU Visits, if last known HIV-1 RNA level is >1000 copies/mL.

c. PhenoSense Integrase and GeneSeq Integrase testing

PhenoSense Integrase and GeneSeq Integrase testing will be additionally performed in conjunction with PhenoSense® GT, if subject has past exposure to an integrase or in cases where complex drug resistance patterns is known or suspected.

*Samples for PhenoSense® GT (and PhenoSense Integrase and GeneSeq Integrase testing, if collected) will be stored at Lab and will be analyzed only if subject experiences virologic failure.*

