3.2 Secondary outcome measures

3.2.1 Exploratory Outcome Measures

- Measurement of treatment adherence to the PRO 140 monotherapy regimen; this will be assessed using number of missed PRO 140 administrations
- Loss of future drug options

The first occurrence of intermediate to high level resistance to any one or more of the standard antiretroviral drugs to which the patient's virus was considered to be sensitive at trial entry (i.e. excluding drug resistance present at baseline).

 - GenoSure Archive Assay will be performed at Baseline.
 - PhenoSense® GT (PhenoSense Integrase and GeneSeq Integrase testing, if applicable), will be performed at the time of virologic failure.
- Proportion of participants overall and within each treatment group experiencing emerging resistance exhibited by fold increase in maraviroc and PRO 140 FC (Fold Change in IC₅₀ and IC₉₀ relative to wild-type virus) between baseline and the time of virologic failure, as a measure of post-baseline phenotypic resistance
 - The data will be from PhenoSense® Entry Assay

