7. DATA CONVENTION AND RELATED DEFINITIONS

7.1 Baseline Definition

For all parameters, baseline will be defined as the last available value prior to initiation of the first dose of PRO140.

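### Drug resistance is tested at Screening and again before dosing at T1, but the SAP's last-value baseline can let resistance reported only at Screening be counted later as a new loss of drug options

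*Protocol*

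**What the plan says.** **Schedule.** Protocol Table 4-1 marks the HIV-1 drug resistance assay at the Screening Visit (SV) and at T1 before treatment. Footnote 12 reads "Monogram Biosciences GenoSure Archive Assay performed at SV and T1", and footnote 11 confirms that the T1 sample precedes dosing: "GenoSure Archive Assay will be performed at Screening and prior to PRO 140 administration at T1 visit". Protocol 7.10.12 gives the same archive-assay schedule, "Frequency of sample collection: At SV, T1, and T48", and adds the virologic failure visit and the 6- and 12-month visits after failure when the last known HIV-1 RNA is below 1000 copies/mL.

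**Baseline.** SAP 7.1: "For all parameters, baseline will be defined as the last available value prior to initiation of the first dose of PRO140".

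**Outcome.** SAP 3.2.1 and Protocol 8.2.3 define loss of future drug options as the first intermediate-to-high resistance to a standard drug "to which the patient's virus was considered to be sensitive at trial entry (i.e. excluding drug resistance present at baseline". For the assays, SAP 3.2.1 says "GenoSure Archive Assay will be performed at Baseline" and that PhenoSense GT "will be performed at the time of virologic failure". It does not mention that there are two pre-dose archive results.

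**Other rules that could apply.** SAP 7.2 handles unplanned duplicates within a single visit. SAP 8.2.3 gives generic descriptive summaries for exploratory outcomes. SAP 8.2.4.4 lists the resistance data by subject. None of them combines SV with T1.

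**The concern.** A last-value baseline suits a quantity that moves over time, such as HIV-1 RNA or CD4 count, where the most recent reading best describes the starting state. Archived resistance is different. Protocol 4.2 places T1 within 6 weeks of SV, and inclusion criterion 3 allows no antiretroviral change between the two visits. If one test reports resistance and the next does not, test variation is a more plausible explanation than a real change in the subject. Keeping only the later result discards information collected before exposure to the study drug.

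The error runs one way. Dropping a positive SV result can only add apparent new losses. Protocol 1.6.1.1 regards selection of variants resistant to other drug classes as unlikely, and says it was not seen in the two earlier monotherapy studies. If few true losses are expected, a small number of misclassified subjects could visibly change a proportion that bears directly on the risk of giving up combination therapy.

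**Working it through.** **Step 1: follow the rules for one drug.** Take a subject with resistance reported at SV, not reported at T1, and reported at a later test.

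- Under SAP 7.1 both results precede dosing and T1 is the last, so the baseline value is not resistant.
- Under SAP 3.2.1 the resistance is not present at baseline, so the exclusion does not apply.
- The later report is then the first occurrence after a non-resistant baseline and is counted as a loss.
- SAP 7.2 does not help, because SV and T1 are different planned visits.
- If the T1 result is missing, SV becomes the baseline and the problem does not arise.

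**Step 2: illustrate the size.** The documents state no detection rate, concordance or prevalence, so there is no plan figure to reproduce. The assumptions are:

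- *s* is the probability that one test reports a resistance that is truly archived;
- errors are independent between tests;
- there are no false positives;
- every carrier has one later test with the same *s*.

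Among carriers of an archived resistance:

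- false loss under the last-value rule (missed at T1, found later) = s(1 − s);
- false loss if either pre-dose test counts (missed at both, found later) = s(1 − s)²;
- removed by the fix (found at SV, missed at T1, found later) = s(1 − s) − s(1 − s)² = s²(1 − s).

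| s | Last-value rule | Either-test rule | Removed by the fix |
|---|---|---|---|
| 0.80 | 0.80 × 0.20 = 16.0% | 0.80 × 0.04 = 3.2% | 0.64 × 0.20 = 12.8% |
| 0.90 | 0.90 × 0.10 = 9.0% | 0.90 × 0.01 = 0.9% | 0.81 × 0.10 = 8.1% |
| 0.95 | 0.95 × 0.05 = 4.75% | 0.95 × 0.0025 = 0.24% | 0.9025 × 0.05 = 4.5% |

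The last column belongs to this point. The first column also includes carriers missed at both pre-dose tests, whom no baseline rule can identify.

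**Step 3: relax the assumptions, at s = 0.90.**

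- *Correlated SV and T1 errors.* With correlation ρ, the SV-positive/T1-negative share is s(1 − s)(1 − ρ). Keeping the later test independent, 8.1% becomes 8.1 × 0.5 = 4.05% at ρ = 0.5 and 8.1 × 0.2 = 1.6% at ρ = 0.8.
- *Retesting only at virologic failure.* If an assumed 30% to 50% of carriers fail and only they are retested, 8.1% becomes 8.1 × 0.3 = 2.4% to 8.1 × 0.5 = 4.05%.
- *No such pattern, or no later detection.* The number is zero.

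**The case against.** The strongest reply is that the miscount follows from one reading of the SAP and is not bound to happen. The outcome turns on whether the virus was considered sensitive at trial entry, a term that neither document defines; the baseline wording only glosses it. Protocol 4.2 has T1 take place once resistance results are available for the investigator to review, which points to SV as the result informing entry. Protocol 4.1.2 also exempts genotype and phenotype from repeat screening tests. An analyst could reasonably treat resistance at SV as present at entry. This stands, and it limits the claim to what the literal baseline rule produces. It also shows that trial entry and SAP baseline may refer to different tests, which is a reason to specify.

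A second reply is that the documents say nothing about the archive assay's sensitivity, specificity or repeatability, so a positive SV call is not proof of resistance. This also stands. The figures above are conditional on stated assumptions, and the fix has to allow for false-positive SV calls.

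Third, SAP 3.2.1 names only PhenoSense GT at failure as the later test, although Protocol 7.10.12 also collects archive samples at T48 and, at low viral load, at failure and the long-term visits. Retesting may therefore reach fewer than all subjects. The change of assay between baseline and failure is a separate source of apparent new resistance, which this fix does not address.

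Finally, the outcome is exploratory, no inference is planned (SAP 7.3 and 7.4), and the SV result stays visible in the listings. That limits the consequence, but a listing does not correct the summarised proportion.

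**Conclusion.** The point holds in a limited form. A stated rule, applied as written, can classify resistance that was already reported before dosing as a new loss. Under independence, no false positives and universal retesting, the avoidable part is 12.8%, 8.1% or 4.5% of carriers at s = 0.8, 0.9 or 0.95. Correlated errors or selective retesting reduce it, possibly to very little. The effect is on a descriptive exploratory proportion; no hypothesis test, power or primary outcome changes.

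A reader might infer that false calls will make up most of the reported losses. The documents do not support this: Protocol 1.6.1.1 calls emergence unlikely but gives no rate, and neither assay performance nor the prevalence of archived resistance is stated. A reader might also infer that the problem disappears only if SV and T1 never disagree. It is also absent when the disagreement runs the other way, when the resistance is not detected again, or when there is no later test.

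**What to change.** Add an exception to SAP 7.1 and repeat it in 3.2.1, for example:

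*For loss of future drug options, resistance to a drug is present at trial entry (baseline) if intermediate or high-level resistance to that drug was reported at SV or at T1. A loss is counted only if such resistance was absent at every available pre-dose test and present at a later test.*

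This also ties trial entry to the same results as baseline. Flag SV/T1 discordance by drug in the SAP 8.2.4.4 resistance listing.

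The cost is a short SAP addition and a derivation on data already scheduled for collection. The downside is that a false-positive SV call could hide a true later loss of that drug; the discordance flag lets the reader see those cases.
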